Under the assumption that the incidence rate of the serious infections is 5.3% as a threshold on the basis of the results of the phase III international joint studies, 553 patients are required to monitor the incidence rate in the post-marketing surveillance with estimation accuracy that enables a power for the 5.3% threshold to be $\geq 80\%$ in case where the real risk exists 1.5 times or more of the threshold. It is considered possible to evaluate occurrence of the serious infections in the special DUI (SDUI) having 600 patients as a target sample size.

The incidence rate of ADRs occurring in one patient was 0.2% in the phase III international joint studies. The power to detect an ADR whose incidence rate of 0.2% is 69.9% in at least one patient out of 600 patients.

5. Planned Number of Medical Institutions by Department

All medical institutions where Benlysta is prescribed (except medical institutions that prescribe Benlysta only for patients aged <15 years since approval for paediatric dosage)

6. Study Period

1. Study conduct

Study period : launch date of Benlysta to three months after termination of the observation period in patients eligible for case report form (CRF) collection (period of the follow-up investigation, if conducted) or lifting date of approval conditions, whichever comes later

Observation period :

The observation period per patient will be 52 weeks from the start of Benlysta administration.

For patients who continue administration at the end of the observation period, conduct the two-year follow-up investigation as much as possible, and monitor occurrence of AEs leading to death, serious infections, PML, and MT.

If a patient has withdrawn from /terminated administration of Benlysta, it will be until the withdrawal/termination.

Scheduled enrolment period : launch date of Benlysta to six months after lifting of approval conditions

Patients are eligible for CRF collection when starting Benlysta administration by 31 October, 2018, and CRFs will be collected as required when patients start the administration since 1 November, 2018. Additionally, patients are eligible for enrolment when starting the administration by the acknowledgment of the report at a committee meeting, where the all-case investigation-related conditions for approval are lifted (except patients aged <15 years who start Benlysta administration since approval for paediatric dosage), and enrolment will continue.

2. Study end

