Continuation status of Benlysta administration at the end of the observation period, the reason if a patient has withdrawn from/terminated administration
14. Possibility of study continuation
Possibility of implementing the two-year follow-up investigation after the end of the observation period (until 3 years after the start of administration) (if a patient continues Benlysta administration at the end of the observation period)
15. Pregnancy
(For female patients) whether or not Benlysta is administered to a pregnant woman, whether or not a patient is pregnant during the observation period and estimated delivery date
In addition, the follow-up investigation should be conducted for a mother and her foetus as far as possible regarding the course of delivery, spontaneous abortion, elective abortion, and AEs, etc.
16. Adverse events (AEs)
Presence or absence of AEs after the start of administration, diagnosis or symptoms, occurrence date, outcome of AEs, outcome date, seriousness, reason for assessing as serious, relationship to Benlysta, factors suspected of being related to AEs except Benlysta
If the events corresponding to the priority study matters occur, the detailed investigation will be conducted about the course of occurrence, therapeutic regimen, etc.
- 1) To grasp the priority study matters and ADRs, the investigator will collect the information about all AEs (e.g., a disease, symptom, abnormal laboratory value) occurring after the start of administration, regardless of whether or not Benlysta is related to an AE. Considering whether or not the possibility of a reasonable relationship to Benlysta is present, etc., the relationship to Benlysta will be assessed on any of “related” or “not related”.
 - 2) The AEs assessed as “related” to Benlysta will be handled as an “ADR” suspected of being caused by Benlysta.
17. Two-year follow-up investigation after the end of the observation period (if Yes in "14. Possibility of study continuation")
Assessment date, presence or absence of AEs leading to death, serious infections, PML, and MT, diagnosis or symptoms, occurrence date, outcome of AEs, outcome date, seriousness, reason for assessing as serious, relationship to Benlysta, factors suspected of being related to AEs except Benlysta

9. Analysis Items and Methods

1. Analysis items

1) Patient disposition-related matters

- i) Number of enrolled patients and number of patients whose CRF is collected and fixed

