6.2.5. Composition ratio of this drug administration status (Table 1.06x, 1.062x)

Analyzed:	Safety analysis set, efficacy analysis set
Analysis details:	
The number and composition ratio (%) and/or summary statistics will be calculated for each analysis set of route of administration, total number of doses, duration of treatment, total dose, and mean dose per administration.
 
For the status of administration of this drug (summary statistics), similar analyses will be performed by initial route of administration (IV, SC) (safety analysis set).
 
Unless otherwise specified, the denominator for the composition ratio (%) will be the total of each analysis set.

For total number of doses (IV), total dose (IV) [mg/kg], and average dose per administration (IV) [mg/kg], the denominator will be the number of subjects dosed by route (IV).

For total number of doses (SC), total dose (SC) [mg], and average dose per administration (SC) [mg], the denominator will be the number of subjects dosed by route of administration (SC).

Items:

- Primary route of administration (IV, SC SC is separated from AI and PFS and unknown)
- Route of administration (IV, SC, change *) *: Number of subjects for IV and SC excluding changes
- Duration of treatment (days) (<28, 28 ≤ to <168, 168 ≤ to <364, 364 ≤, unknown)
- Total number of infusions (IV) (<6, 6 ≤ to <11, 11 ≤ to <15, 15 ≤, unknown)
- Total number of SC injections (<13, 13 ≤ to <25, 25 ≤ to <37, 37 ≤ to <52, 52 ≤, unknown)
- Total dose (IV) [mg/kg] (≤ 50, 50 < to ≤ 100, 100 < to ≤ 140, 140 <, unknown)
- Total dose (SC) [mg] (≤ 2400, 2400 < to ≤ 4800, 4800 < to ≤ 7200, 7200 < to ≤ 10200, 10200 <)
- Mean single dose (IV) [mg/kg] (<10, 10, 10 <, unknown)
- Mean dose per administration (SC) [mg] (<200, 200, 200 <, unknown)

6.2.6. Duration of this drug treatment by reason for treatment discontinuation/completion 1.07 (Figure 1.02, 1.021)

Analyzed:	Safety analysis population

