6.3.2. Time to onset of adverse reaction/event (Tables 2.021~2.024, 2.061~2.065, Figure 2.01~2.05)

Analyzed: Safety analysis population, safety analysis population (patients for whom follow-up survey forms were collected)

Analysis details: The proportion of each SOC and PT will be tabulated by category of number of days to onset of adverse reaction/adverse event for each PT (weeks). In addition, the incidence of adverse reactions/adverse events and the cumulative incidence of adverse reactions/adverse events will be tabulated for all subjects and serious adverse reactions/adverse events.

The proportion will be presented by number of days as the sum of cases excluding overlapping adverse reactions/adverse events.

The cumulative percentage of cases by number of days will be presented. However, each case counts only in days for its first occurrence (first reaction/AE). "Unknown" in the same case shall be counted preferentially.

As for the order of output, data will be output in the descending order of the number of subjects by SOC in the total column, in the descending order of the number of subjects by PT, and in the order of PT codes.

Also, For the incidence of adverse events/serious adverse events (number of events/number of patients), a bar graph will be prepared for each category of time to onset (weeks). Similar bars will be produced for Hypersensitivity, Hypersensitivity "Infections (Including tuberculosis, pneumonia, pneumocystis pneumonia, sepsis, and opportunistic infection)," Hypersensitivity "Depression, suicidal ideation, suicide attempt" and Malignancy. However, "Depression, suicidal ideation, suicide attempt" and "malignant tumors" are handled as adverse events only.

The number of days with onset is calculated as follows.

Date of onset - date of start of treatment +1 (7 days is counted as 1 week)

*SOC and PT are summarized by SOC and PT, respectively, of initial onset.

*This should be done in the same way for events collected as follow-up (Table 2.061-2.065).

Time (weeks) to onset of adverse reaction/adverse event category: • <2, 2 ≤ to <4, 4 ≤ to <8, 8 ≤ to <12, 12 ≤ to <16, 16 ≤ to <20, 20 ≤ to <24, 24 ≤ to <28, 28 ≤ to <36, 36 ≤ to <44, 44 ≤ to <52, 52 ≤, unknown

event category:

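### Serious infections, PML, malignancies and deaths that begin after Benlysta is stopped are not systematically collected, and the SAP's event and person-time windows do not match

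*Protocol*

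**What the plan says.** **Observation.** Protocol section 6 first sets a common length: "The observation period per patient will be 52 weeks from the start of Benlysta administration". It then shortens it for patients who stop Benlysta: "it will be until the withdrawal/termination". Section 7.4 has the CRF handed in at that point and asks for telephone contact about AEs only within the observation period. Neither document provides a post-treatment safety window or a vital-status check.

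**Follow-up.** Section 6 continues: "For patients who continue administration at the end of the observation period, conduct the two-year follow-up investigation as much as possible". The events followed are AEs leading to death, serious infections, PML and malignant tumours. Section 8 item 14 repeats the condition, "if a patient continues Benlysta administration at the end of the observation period", and item 17 depends on item 14.

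**What is collected.** Section 8 item 16 asks for all AEs "occurring after the start of administration, regardless of whether or not Benlysta is related to an AE" and names no end date of its own.

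**How it is analysed.**
- SAP 4.15 defines AEs as events entered in Argus. Its 52-week set runs to the day of first dose + 364, with no cut at stopping.
- SAP 5.2 divides by the number of patients analysed.
- SAP 5.5 defines patient-years as the sum of treatment durations, and SAP 6.3.8 applies this to AEs, ADRs and the safety specification items.
- The follow-up tables (SAP 6.3.2, 6.3.3 and 6.3.6) use the "safety analysis population (patients for whom follow-up survey forms were collected").

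**The concern.** The purpose in Protocol section 1 is long-term safety in daily practice, with no restriction to patients who stay on treatment. The priority events include some that may lead to stopping or may appear only after it. If collection closes on the stop date, an infection, tumour or death with its first sign some weeks later depends on spontaneous reporting.

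Three things are at stake:
- A patient watched for 10 weeks enters the denominator of a crude 52-week proportion on the same footing as one watched for 52, and counts as event-free if nothing was recorded. For this statistic the cut can only remove patients with events.
- The years 1 to 3 tables describe people who survived and stayed on Benlysta for a year, but they could be read as the long-term experience of everyone treated.
- A post-stop event that does reach Argus can enter a person-year numerator whose denominator holds none of that patient's off-drug time.

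**Working it through.** **1. The plan's own figures.** Protocol section 4 gives a 5.3% threshold (25/470), a 1.5-fold increase (1.5 × 5.3% = 7.95%), power of at least 80%, and 553 patients. Alpha is not stated. An exact one-sample binomial test at one-sided 5% reproduces 553: with a critical count of 39, alpha is 4.5% and power 80.3% (552 patients give 79.99%). The rare-ADR figure also reproduces: 1 − 0.998^600 = 69.9%. Neither figure is in dispute.

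**2. Effect on the crude 52-week proportion.** Assumptions, none supplied by the documents: a share d stops, stop times are uniform over the year, the hazard is constant and equal on and off drug, and no post-stop event is reported.
- Hazard for a true 5.3%: λ = −ln(1 − 0.053) = 0.0545 per year.
- Mean risk captured in a patient who stops: 1 − (1 − e^−λ)/λ = 1 − 0.053/0.05446 = 2.67%.
- Recorded proportion: d × 2.67% + (1 − d) × 5.3%.
- Unobserved patient-years among 600: 600 × d × 0.5 in year 1 and 600 × d × 2 in years 2 and 3.

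| d | Recorded proportion | Patients with an event missed per 600 | Unobserved year 1 | Unobserved years 2–3 |
|---|---|---|---|---|
| 15% | 4.91% | 31.8 − 29.4 = 2.4 | 45 | 180 |
| 25% | 4.64% | 31.8 − 27.9 = 3.9 | 75 | 300 |
| 35% | 4.38% | 31.8 − 26.3 = 5.5 | 105 | 420 |

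The same formula at a true 7.95% gives recorded proportions of 7.36%, 6.97% and 6.58%. With 600 patients and a critical count of 42, power is 82.5% under full observation and 65.5%, 51.1% and 36.1% at these stopping shares. This is an illustration of sensitivity, not an estimate of the study's power.

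**3. Effect on the person-year rate.** Under the same assumptions, if only on-drug events are counted, the expected number is λ × on-drug years. At d = 25% that is 28.6 events over 600 × (1 − 0.125) = 525 patient-years, or 5.45 per 100, the true rate. The cut does no harm here.

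**4. Effect of the window mismatch.** Now suppose every post-stop event up to Week 52 did reach Argus. The numerator becomes 600 × λ = 32.7 while the denominator stays at on-drug time, so the rate is multiplied by 1/(1 − d/2): 1.08, 1.14 and 1.21 at 15%, 25% and 35%. That is 5.9, 6.2 and 6.6 per 100 patient-years against a true 5.45. Actual reporting lies somewhere between none and all, so the crude proportion can be too low while the person-year rate is too high.

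**5. Passages side by side.** SAP 4.12 shows that the SAP cuts data at the end of treatment when it intends to: steroid data after the end date are left out. SAP 4.15, 5.5 and 6.3.8 contain no such rule for AEs.

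**The case against.** The strongest reply has five parts.

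*Events in patients who stop are not simply lost.* This stands. Anything with onset before the stop date is collected. Item 16 takes symptoms as well as diagnoses, together with outcome, and priority events get a detailed investigation. A cough or neurological sign that led to stopping is therefore inside the window; at most its later diagnosis could be missed. A reader might infer that these events go uncounted in everyone who stopped, but the documents support only that events with onset after stopping are not systematically sought.

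*Item 16 does not contradict section 6.* Largely right. Item 16 lists what is recorded; sections 6 and 7.4 set the window. The +364 rule in SAP 4.15 can be read as an upper limit for a table, and the change history says the 52-week report in 6.3.6 was added for comparison with overseas studies. What survives is that the SAP's event and time windows differ.

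*Exposure-adjusted rates are planned.* This stands, as step 3 shows, provided that stopping is unrelated to risk and the numerator is limited to on-drug events. It does not help with late malignancy, PML or death.

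*The size is assumed.* This stands. The loss would be smaller if risk falls after stopping and larger if it rises around stopping; the documents settle neither. Nor do they say how the trials behind the 5.3% were observed. A further temptation is to read the infusion-count classes in SAP 6.2.5 as proof that closure misses part of a dosing interval. Those are table cut-points, and the Protocol does not equate withdrawal with the last administration.

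*It is too late to redesign collection.* Mostly right. Protocol version 4.2 is dated 27 June 2025 and final analysis is due July 2025. Patients routinely eligible for CRF collection started by 31 October 2018, so their third year ended by 31 October 2021. The analysis and labelling changes remain possible before the December 2025 report.

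**Conclusion.** The point holds as a limited, cheaply improved weakness. Events of the four follow-up types that begin after stopping are not systematically collected, and the long-term tables describe only patients continuing at Week 52 whose forms were collected.

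The crude 52-week proportion can understate risk: 5.3% recorded as about 4.9% to 4.4%, or roughly 2 to 6 patients with a serious infection per 600. This rests on an assumed 15% to 35% stopping share, even stopping, a constant hazard on and off drug, and no reporting after the stop. On-drug person-year rates are unaffected by this mechanism if stopping is unrelated to risk, but as written they can mix post-stop events with on-drug time.

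The documents do not support a claim that the sample size is wrong, that the bias has a known size, or that follow-up to Year 3 should now be rebuilt for closed patients.

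**What to change.** 1. **SAP 4.15, 5.5, 6.3.8.** Using the stop and onset dates already held, classify each event as on-treatment or post-treatment and show both. Restrict the numerator of the person-year rates to events within the on-drug time in the denominator, or extend both by the same fixed window. State how events with unknown onset are handled, since SAP 4.15 places them within Week 52.
2. **Follow-up tables 2.061–2.065, 2.071x, 2.073x.** Title them as patients continuing Benlysta at Week 52, alongside the existing form-collected label, and limit the long-term safety conclusion to that group.
3. **Any patient whose CRF is still open.** Continue AE collection for a fixed period after the last dose, with the length set by the sponsor. Record the four follow-up events on the existing Follow-up CRF as far as possible, whether or not Benlysta continues. Reconcile section 6 and items 14 and 17 accordingly.
4. **Closed patients.** State in the final report that post-stop events were not systematically collected, and give the number who stopped and when; SAP 6.2.6 already produces this.

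**Cost.** Items 1, 2 and 4 need programming and wording only. Item 3 needs a protocol change, with advance notification to the PMDA unless it counts as minor (section 15.1), and site effort for whichever patients remain open. Some post-treatment events will reflect later therapy, which the split makes visible but does not remove, and some patients will be unreachable.

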6.4.14.	Time course of percent improvement in steroid group (Figure 3.05) 35
6.4.15.	Changes in laboratory values (Anti-dsDNA, C3, C4, CH50, protein/creatinine ratio) (mean + SD) (Figure 3.06x) 35
6.4.16.	Changes in the proportion of patients receiving immunosuppressants (Table 3.15)..... 35
6.5.	List/fixed form 36
6.6.	Exploratory Analyses 36
CCI 36
 38
 38
 39
6.7.	Additional tabulation for MA 39
7.	Appendix 40
8.	Document Change History..... 40

1. Objectives of the survey

This Surveillance will be conducted to collect and evaluate information on the long-term safety and efficacy of Benlysta for I.V. Infusion and Benlysta for S.C. Injection (Hereinafter referred to as this drug) under the actual use conditions.

2. Software and Dictionaries

2.1. Statistical analysis and tabulation software

	Software and Version
OS	Microsoft Windows 10
Statistical analysis software	SAS Ver.9.4
Tabulation software	Microsoft Excel 2016

2.2. Dictionary

Item	Dictionary name
Name of disease (complication), name of adverse event, name of adverse reaction	MedDRA/J (* The version of MedDRA to be used shall be reviewed and determined by the team at each time of reporting.)
Name of drug, drug	GSKdrug (Data will be tabulated using the version used for coding by DM. * In principle, use the latest one.)

3. Definitions of Terms

Term	Definition
Start date of administration of this drug (registration form)	“Start date of administration of this drug” in the registration form
Start date of this drug	First administration start date recorded in the “Administration status of this drug” in the survey form
SELENA SLEDAI	Safety of Estrogens in Lupus Erythematosus National Assessment SLE Disease Activity Index
PGA	Physician's global assessment
LLDAS	Lupus Low Disease Activity State
LOCF	Last observation carried forward
PML	Progressive Multifocal Leukoencephalopathy

4. Case and Data Handling

4.1. Sample size

- ✧ Number of patients: Number of patients meeting applicable conditions.

4.2. Analysis sets/sites

Item	Definition
Registered sites	Sites for all registered patients (patients eligible for registration). Sites with patients registered before the data lock date (excluding duplicate site codes).
Enrolled patients	Patients enrolled within the enrollment period specified in the protocol (from December 13, 2017 to the date of lifting of approval conditions) (registration-eligible patients). Subjects with an enrollment date before the data lock date.
Patients with locked CRF	All registered patients whose CRFs were collected and locked. Cases that have a recall date and a processing completion date and the processing completion date is before the data lock date.
Safety analysis population	Patients with locked CRFs who do not correspond to patients excluded from the safety analysis set (see 4.3.1)
Efficacy analysis population	Patients in the safety analysis set who are not excluded from the efficacy analysis set (see 4.3.2)
CRF collection target patients (Approval condition lifting)	Reports on registered patients whose CRFs were collected and patients eligible for CRF collection were identified (administration of this drug was started by October 31, 2018). The start date of administration of this drug (registration form) shall be the date of registration form.
Sites that can publish	PMW sites that are “11 _ Publication allowed (already concluded) ” or “ 13_ Publication allowed (no change required) ” and sites that are confirmed as “21 _ Being confirmed ” to be “ Publication allowed ”

Item	Definition
Subjects who completed the observation period (Interim analysis)	
< Subjects falling under Population A >
 
Disclosure-ready patients meeting any of the following conditions among patients treated with this drug before October 31, 2018 at study sites
 
 • Completed up to Week 52: Separate Volume 1 (official approval) and Separate Volume 2 (official approval) • Completed as discontinued: Volume 1 (official approval) in which the reason for discontinuation is described is official approval (excluding official approval of Volume 2 only) • Completed as discontinued (logic assessment): Separate volume 1 (official approval) and Separate volume 2 is “Unnecessary ” or“ Unable to collect ” 
< Subjects falling under Population B >
 
This falls under “patients with depression-related events ” among patients whose CRFs were additionally collected and are specified in a separate document.

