Completion of final analysis : July 2025

Completion of final report writing : December 2025

7. Study Methods

1. Requirements for supply

For supply, confirm that medical institutions and physicians meet the following requirements.

1) Requirements for medical institutions

Medical institutions sufficiently capable of taking emergency measures, including infections, such as pneumonia, sepsis, and TB

2) Requirements for physicians

Physicians who correspond to any of the following;

1. Certified as a rheumatologist and an attending rheumatologist, experienced in the treatment of SLE
2. Specialised in rheumatic disease, certified as an intractable disease designated physician and cooperated intractable disease designated physician, experienced in the treatment of SLE
3. Sufficiently experienced in the treatment of SLE, providing the treatment of SLE in proper cooperation with physicians who correspond to the above-mentioned
4. Providing the treatment of SLE under direct supervision of physicians who correspond to 1 and 2

The person in charge of the study (medical representative or monitoring outsourcee) will visit medical institutions before supply, explain to the planned physicians for prescribing Benlysta, etc. that Benlysta is obligated to conduct an all-case investigation, obtain the Confirmation Letter from them (head physicians) as confirmation.

2. Request and contract for the study

- 1) The person in charge of the study will explain the objectives, target population, study items, study methods, etc. to the planned physicians for the study, etc. at medical institutions by/to which Benlysta is adopted/supplied, and will request them to cooperate with the study.
- 2) If cooperation to the study has been obtained, the Written Contract should be concluded with the heads (e.g. directors, etc.) of the medical institutions before the start of the study.

3. Enrolment of target population

The study will be conducted using an all-case investigation method.

- 1) The investigator will record the patient information, etc. about patients eligible for enrolment in the Enrolment Form, and will fax it to the Enrolment Centre or submit it to the person in charge of the study immediately after the start of administration. The personally identifiable information, such as the name, address, date of birth, initials of patients, should not be recorded in the Enrolment Form.
<Enrolment Centre>

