 - 2) After approval of Benlysta, the Written Contract should be concluded before the start of administration in principle, however, patients to whom Benlysta has unavoidably been administered before the conclusion of the contract will be also enrolled as a retrospective patient.
4. Data collection and case report form (CRF) completion
- 1) The investigator will confirm the study items, such as the characteristics of patients eligible for CRF collection.
 - 2) During the observation period, the investigator will monitor the information about safety and effectiveness, etc. If an enrolled patient does not visit the hospital during the observation period, the investigator will monitor the information about AEs and others by telephone, etc. as far as possible.
 - 3) The CRF consists of three CRFs to maximum, and the observation period per CRF will be defined as below.
 - CRF 1 : Week 1 to 24 after the start of administration
 - CRF 2 : Week 25 to 52 after the start of administration
 - Follow-up Investigation CRF : Year 1 to 3 after the start of administration
 - 4) The investigator will record the obtained information on the CRF. At the end of the observation period of enrolled patients for each CRF (or at withdrawal/termination, if a patient has withdrawn from /terminated administration of Benlysta), submit the completed CRF to the person in charge of the study. The personally identifiable information, such as the name, address, date of birth, initials of patients, should not be recorded in the CRF.
5. Confirmation of all-case investigation implementation
- Annually and after the end of the study period, the investigator will confirm whether or not enrolled patients are all receiving Benlysta, affix his/her signature or name/seal to the "Confirmation Letter of All-Case Investigation" and submit it to the person in charge of the study.

8. Study Items

The investigator will collect the information about the following items, etc. as far as possible and record it on the CRF.

1. Information about a medical institution
Name of a medical institution, department, investigator
2. Patient characteristics (at the start of administration of Benlysta)

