4.3. Analysis Exclusion Criteria

4.3.1. Patients excluded from safety analysis

If there are overlapping reasons for exclusion and the reasons for exclusion should be prioritized, the reasons for exclusion from the safety analysis should be assigned in the following order:

Code	Safety Excluded from analysis	Priority Rank	Conditions for exclusion	Logic Judgment
S1	Outside the survey/registration period	1	
 • The date of completion of administration of this drug/the date of last observation is outside the survey period • Date of enrollment is outside the enrollment period 	○
S2	Outside the contract period	2	
 • The date of registration is outside the contract period. 	○
S3	This drug naïve	3	
 • Patients with no description at all in the Dosage and Administration section of this drug or all descriptions of dosage are 0 	○
S4	No visits after first dose (SC only)	4	
 • The reason for discontinuation/completion of administration in the [Status of continuation of administration of this drug at the end of the observation period] is "No 	○

Code	Safety Excluded from analysis	Priority Rank	Conditions for exclusion	Logic Judgment
			visits after the first dose"	
S5	Adverse event data missing	5	• Cases for which [Presence/absence of adverse event] is “Unknown ” or blank and there is no adverse event data	○
S6	Same case (co-examination/hospital transfer)	6	• A case judged to be the same case after consultation/transfer to another hospital	×
S7	Same case (duplicate description)	7	• Cases in which the same information is entered redundantly and judged to be the same case	×
S8	Others (safety)	8	• Exclusion items determined by the case review committee for reasons other than the above	×

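### SAP 4.2 closes the enrolment period at lifting of the approval conditions, six months before the protocol does, so eligible patients registered late drop out of the enrolled count

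*SAP*

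**What the plan says.** Protocol section 6 sets two separate cut-offs.

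- For registration: "Scheduled enrolment period : launch date of Benlysta to six months after lifting of approval conditions".
- For treatment start: "patients are eligible for enrolment when starting the administration by the acknowledgment of the report at a committee meeting", which is the meeting at which the all-case conditions are lifted (called lifting below).

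Protocol section 7.3 has registration follow the first dose. The investigator faxes the enrolment form or is to "submit it to the person in charge of the study immediately after the start of administration". A patient treated before the contract was concluded "will be also enrolled as a retrospective patient".

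SAP 4.2 defines enrolled patients as "Patients enrolled within the enrollment period specified in the protocol", and its parenthesis then gives that period as "from December 13, 2017 to the date of lifting of approval conditions". It also requires an enrolment date before data lock and notes in a further parenthesis that these are patients eligible for registration.

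SAP 4.3.1 lists, as the second condition of exclusion S1, "Date of enrollment is outside the enrollment period". It gives no dates of its own. S1 is marked as decidable by logic, unlike S6 to S8.

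**The concern.** The SAP cites the protocol as the source of its enrolment period and then misstates it by six months. In effect it applies the protocol's treatment-start cut-off to the registration date. Since registration comes after the first dose, some patients who started shortly before lifting can be expected to register after it. The protocol's extra six months leaves room for them.

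Two outputs depend on the date. The number of enrolled patients is a stated analysis item (Protocol 9.1 1) i)) and stands near the top of the Figure 1.01 flow chart. The all-case investigation is a condition of approval, so this count helps to document that the condition was met. Second, S1 would take any affected patient with a locked CRF out of the safety set. That patient's adverse events would then appear only in the listing for excluded patients (Listing 7), and the recorded reason, registration outside the period, would be wrong under the protocol.

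**Working it through.** **Figures in the plan.** The plan gives no figure for the enrolment window or for registrations after lifting. Its sample-size figures reproduce and do not use the enrolment date:

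- With p1 = 1.5 × 0.053 = 0.0795, power 80% and an assumed two-sided 5% level, n = (1.960 + 0.842)² × (1 − 0.0795)/0.0795 ÷ (ln 1.5)² = 552.8, rounded up to the protocol's 553.
- 1 − (1 − 0.002)^600 = 69.9%, as stated.

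**The two windows side by side.**

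| | Protocol section 6 | SAP 4.2 |
|---|---|---|
| Window opens | launch | 13 December 2017 |
| Treatment must start by | lifting | not in the period itself; left to registration eligibility |
| Registration must occur by | lifting + 6 months | lifting + 0 months |

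The gap at the end is 6 − 0 = 6 months.

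**A test case.** A patient starts treatment one week before lifting and is registered three weeks after starting, that is, −1 + 3 = 2 weeks after lifting. Under the protocol the start is in time and the registration is in time, so the patient is eligible and enrolled. Under SAP 4.2 the enrolment date falls after the period ends, so the patient is not counted. If a CRF was locked, S1 applies.

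**Who in the safety set could be affected.** The safety set needs a locked CRF (SAP 4.2).

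- CRFs are routine only for starts by 31 October 2018 (Protocol section 6). The SAP change history adds a flow chart for the lifting on 23 December 2022 and forms for inquiries on the lifting report on 30 September 2024. If lifting was no earlier than December 2022 (an inference, since the date is not given), a routine-CRF patient would be caught only if registered more than four years after the first dose.
- For later starters, CRFs are collected only as needed. The one such collection that the SAP describes is the depression-event forms from October 2023. SAP 4.19 already excludes these from the safety analysis in regulatory documents submitted after June 2024.

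**Scale for the enrolled count.** With steady registration over D months and a lag of L months from first dose to registration, the share registered after lifting is about L/D. The documents give neither value. Taking D = 80 as an assumption:

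- L = one week: 0.23/80 = 0.3%
- L = 1 month: 1/80 = 1.25%
- L = 2 months: 2/80 = 2.5%

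These show scale under assumed inputs and are not estimates for this study.

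**The case against.** The best defence is that the SAP names the protocol's period as its own and S1 states no dates, so both could be programmed to the protocol window. In addition, SAP V13.0 (30 September 2024) predates protocol V4.2 (27 June 2025) and may match a version that is not available here. Neither removes the problem. If the protocol governs, the parenthesis is simply wrong, and a programmer may well code the date that is printed. Whatever the history, the protocol schedules the final analysis for completion in July 2025, after V4.2, so the two documents should agree.

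Other parts of the defence do stand, and they limit the point. A reader might infer any of the following, which the documents do not support:

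- *Safety incidence is materially distorted.* The group with locked CRFs that S1 could wrongly remove looks almost empty, for the reasons given in the working.
- *Figure 1.012 is wrong too.* It is labelled as the analysis for the lifting itself, so its data would be expected to be locked before any post-lifting registration.
- *The SAP also fails to reproduce the start-date limit and the exclusion of under-15s who start after paediatric approval.* Its note that enrolled patients are those eligible for registration reasonably carries in both rules.
- *Retrospective patients surface mainly at the final confirmation and are all lost.* The protocol defines them by treatment before contract, and the all-case confirmation is annual as well as final.
- *S1's first rank makes the loss worse.* Rank only decides which reason is shown when several apply.

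**Conclusion.** The mismatch is real in the current text. SAP 4.2 ends the enrolment period six months before the protocol section it relies on, and S1 acts on the same date. Followed as written, patients who started by lifting and were registered in the next six months are left out of the enrolled-patient count and Figure 1.01. Any of them with a locked CRF would be excluded from the safety set for a reason that does not hold under the protocol. Patients who first start after lifting are not part of this, because the protocol does not make them eligible.

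The number affected cannot be computed without the lifting date and the registration counts. A figure of 1 to 2.5% of the enrolled count is tempting, but it rests on an assumed lag and duration, and a lag of months sits poorly with a form due promptly after the first dose. The main effect is on the enrolled count. The effect on safety incidence is probably very small, provided that lifting was not before December 2022 and that no later CRF collection exists beyond the one in SAP 4.19. No effectiveness estimate or sample-size figure is shown to change.

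**What to change.** In SAP 4.2, change the end of the enrolment period to six months after lifting of the approval conditions, as in Protocol section 6. In SAP 4.3.1, state that the enrolment period in S1 is that same window. Then regenerate Figure 1.01.

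Do not add a first-dose condition to S1. The change history for SAP V2.0 records that the sponsor deliberately deleted a treatment-start condition from S1 and S2 because this is an all-case surveillance.

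The cost is two wording changes, one adjustment to a logic check and a rerun of one figure. The SAP already uses the enrolment date, so no new data are needed.
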